6.3.6 Assignment and Allocation

Participants enrolled in this study will be randomized in a 1:1:1 ratio to the 30 mg ASP0367, 75 mg ASP0367 or placebo arm.

Randomization will be performed according to the schedule obtained via the IRT system and stratified by site group (2 level: Mayo clinic_Minnesota; Non-Mayo clinic_Minnesota). The study site personnel will dispense either ASP0367 or placebo according to the IRT system's assignment. Specific procedures for randomization through the IRT system are contained in the study procedures manual.

6.4 Investigational Product Compliance

Participants should be counseled on the need to meet 100% compliance with IP. Investigator or designee should ensure that participants meet this goal throughout the study. Participant compliance with IP will be assessed at each visit. Compliance will be assessed by counting returned tablets. Deviations from the prescribed dose regimen will be recorded. When IP is administered at the study site, it will be administered under the supervision of study personnel.

6.5 Dose Modification

Dose modification for individual participants is not allowed.

Dosing may be interrupted if further evaluation is required for ongoing AE(s), clinical laboratory abnormality or intercurrent illness. The investigator will assess the resolution of the event and determine, in consultation with the medical monitor, whether resuming dosing or continued participation in the clinical study is in the best interest of the participant.

6.6 Continued Access to Investigational Product After the End of the Study

Access to ASP0367 will not be available after the end of this study. The compound is still in an early phase of clinical development prior to the determination of the safety and efficacy data that would support continued development with the dose selected and the intent to pursue marketing approval.

6.7 Treatment of Overdose

Any dose of IP greater than 75 mg/day will be considered an overdose. This overdose level may be adjusted based on emerging safety and tolerability data.

Sponsor does not recommend specific treatment for an overdose.

In the event of an overdose, the investigator should:

- Contact the medical monitor immediately.
- Assess the participant and provide appropriate supportive care as needed.
- Evaluate the participant along with safety information available to determine, in consultation with the medical monitor and the sponsor, whether study treatment should be discontinued.
- Document the quantity of the excess dose as well as the duration of the overdose.

Refer to [Section 10.3.7 Reporting Procedures for Special Situations] for reporting requirements for suspected overdose or other medication error.

6.8 Concomitant Therapy

6.8.1 Previous and Concomitant Treatment

The investigator must record the use of all previous and concomitant treatment from 3 months prior to randomization to follow-up visit in the CRF, both medication and nonmedication therapy. The investigator may record the use of previous treatment before 3 months prior to randomization in the CRF as long as participants remember. Previous and concomitant treatment includes all vitamins, herbal remedies, over the counter and prescription medications, as well as exercise regimen and physical therapy.

6.8.2 Prohibited Concomitant Treatment

- PPAR ligands listed in [Section 10.5 Appendix 5 List of Excluded Concomitant Medications] are not allowed within 4 weeks prior to randomization and during the study.
- Substrates for P-gp, BCRP, OATP1B1, OATP1B3 and organic anion transporter (OAT)3 are not allowed during the study. For participants using atorvastatin, rosuvastatin and simvastatin, switching to a less-interacting statin (pravastatin, pitavastatin and lovastatin) is allowed at investigator's discretion.
- Moderate and strong inhibitors of CYP3A are not allowed during the study.
- Inhibitors for transporter BCRP are not allowed during the study.
- Inhibitors of UGT1A3, UGT1A8 and UGT1A9 are not allowed during the study.

- Strong and moderate inducers of CYP3A and inducers for UGT1A3, UGT1A8, UGT1A9 and transporters are not allowed during the study.
- Triheptanoin, a synthetic medium chain triglyceride indicated in long-chain FAO disorders, is not allowed during the study.

A list of prohibited medications is provided in [Section 10.5, Appendix 5: List of Excluded Concomitant Medications].

6.8.3 Restricted Concomitant Treatment

CoQ10, carnitine, creatine or other mitochondrial disease-focused vitamins or supplemental therapies for the treatment of symptoms of the mitochondrial disease must be stable for 3 months prior to randomization and for the duration of the study.

6.8.4 Other Restrictions

See [Section 5.3 Lifestyle Considerations].

7 STUDY PROCEDURES AND ASSESSMENTS

- Study procedures and their timing are summarized in the schedule of assessments [Table 1]. Adherence to the study design requirements, including those specified in the schedule of assessments, is essential and required for study conduct. Prospective protocol waivers or exemptions are not allowed.
- Any change, divergence or departure from the study design or procedures identified in the protocol is considered a protocol deviation. All deviations from the protocol are to be recorded.
- Immediate safety concerns should be discussed with the sponsor immediately upon occurrence or awareness to determine if the participant should continue or discontinue study treatment.
- All screening evaluations must be completed and reviewed to confirm that potential participants meet all eligibility criteria. The investigator will maintain a screening log to record details of all participants screened and to confirm eligibility or record reasons for screening failure, as applicable.
- Procedures conducted as part of the participant's routine clinical management (e.g., imaging, blood count) and obtained before signing of the ICF may be utilized for screening or baseline purposes provided the procedures met the protocol-specified criteria and were performed within the time frame defined in the schedule of assessments.
- Laboratory/analyte results that could unblind the study will not be reported to investigative sites or other blinded personnel until the study has been unblinded.

7.1 Efficacy Assessments

7.1.1 6-minute Walk Test

The 6MWT will be performed indoors, along a long, flat, straight, enclosed corridor with a hard surface that is seldom traveled. The total distance walked by a participant, as well as

distance per minute will be calculated by rounding to the nearest meter and recorded. The 6MWT will be video recorded for quality purposes unless restricted by policies of the study site.

Participants will be asked to wear comfortable clothing and appropriate shoes for walking. A light meal is acceptable before early morning or early afternoon tests. Participants will be asked to refrain from strenuous exercise on the day preceding and on the day of the 6MWT. A "warm-up" period before the test will not be performed. Participants will sit at rest in a chair located near the starting position for at least 10 minutes before the test starts. The test will be performed as outlined in the schedule of assessments [Table 1].

The "1000 Norms Project Consortium" has established normative distance walked 6MWT data based on age, gender, weight, and height [McKay et al, 2017]. Study participants who walked longer than the distance that 85% of healthy people can walk based on "1000 Norms Project Consortium" at the baseline visit (week 0) can be considered as normal and will be excluded from the study. Each participant's individual z-score will be calculated by entering age and gender, as well as distance walked in 6MWT at baseline (week 0) as indicated at "1000 Norms Project Consortium" website (https://clinicaloutcomemeasures.org/). The z-score > - 1.03 corresponds to the distance longer than 85% of healthy people can walk.

7.1.2 5 Times Sit to Stand

For the 5XSTS, the participant will be instructed to sit with arms folded across their chest and with back against the chair and will be asked to stand up and sit down 5 times in a row, as quickly as he/she can. The instructor will make sure that the participant will stand up fully and try not to let his/her back touch the chair between each repetition. The duration from the time instructor indicates "Go" until the time participant's body touches the chair following the fifth repetition will be recorded. If a participant is unable to complete the first sit to stand independently, without use of arms, the test will be terminated. The test will be performed as outlined in the schedule of assessments [Table 1].

7.1.3 Quality of Life in Neurological Disorders

The Quality of Life in Neurological Disorders (Neuro-QoL) is a measurement system that evaluates and monitors the physical, mental and social effects experienced by adults and children living with neurological conditions. Participants will report Neuro-QoL Item Bank v1.0 Fatigue Short Form and Lower Extremity Function (Mobility) Short Form, which consists of 8 items each. Neuro-QoL will be performed as outlined in the schedule of assessments [Table 1].

7.1.4 Modified Fatigue Impact Scale

The Modified Fatigue Impact Scale (MFIS) is a modified form of the Fatigue Impact Scale. The questionnaire specifically measures how fatigue impacts the lives of those affected by fatigue-like symptoms. There are 21 items in the scale measuring 3 domains of fatigue including physical, cognitive and psychosocial functioning. MFIS will be performed as outlined in the schedule of assessments [Table 1].

7.1.5 Patient Global Impression of Change

The Patient Global Impression of Change (PGIC) scale evaluates the participant's most bothersome symptom and assesses if there has been an improvement or decline in clinical status. The participant will rate his/her change on a 7-point scale. PGIC will be performed as outlined in the schedule of assessments [Table 1].

7.1.6 The Patient Global Impression of Severity

The Patient Global Impression of Severity (PGIS) is a questionnaire designed to assess patient's impression of disease severity. The questionnaire asks the participant to best describe the severity of the participant's most bothersome pre-defined symptom over the past week. PGIS will be performed as outlined in the schedule of assessments [Table 1].

7.1.7 5-level EQ-5D Version (EQ-5D-5L)

European Quality of Life (EuroQol) 5-Dimensions, 5-Level Questionnaire (EQ-5D-5L) is a brief, generic health-related quality of life assessment that can also be used to incorporate participant preferences into health economic evaluations. The EQ-5D-5L descriptive system comprises the following 5 dimensions: mobility, self-care, usual activities, pain/discomfort and anxiety/depression. Each dimension has 5 response levels: no problems, slight problems, moderate problems, severe problems and extreme problems/unable to perform the activity. In addition, it does record the patient's self-rated health on a vertical visual analogue scale with response options ranging from 0 (worst imaginable health) to 100 (best imaginable health). The EQ-5D-5L will be performed as outlined in the schedule of assessments [Table 1].

7.1.8 Primary Mitochondrial Myopathy Video Assessments

Effective with implementation of Protocol Version 8.0 (Substantial Amendment 7), PMMVA will no longer be collected. The Primary Mitochondrial Myopathy Video Assessments (PMMVA) tool provides a standardized way to document and assess patient quality of movement. A caregiver or a close observer will video record specific movement tasks at home using a secure mobile application. In addition to assigned movement tasks, the participant will complete one participant-choice activity. All participants will also have the option to submit a new ability video (if applicable). The participant-choice activity is an activity that the participant will select prior to baseline data capture that the participant is struggling with. The caregiver/observer will video record the same participant's choice activity at each subsequent time point throughout the study. If the participant gains a new ability during the study, the caregiver/observer may video record the new ability at any time during the study in the study mobile application.

7.1.9 Individualized Activity Assessments

Effective with implementation of Protocol Version 8.0 (Substantial Amendment 7), individualized activity assessments will no longer be collected. Participants will identify 3

activities during the screening period that are difficult due to their PMM and/or make them notice their PMM. They will rate the magnitude of interference of their PMM symptoms in the previous 2 weeks for each of their 3 identified activities and the change in ease/difficulty of performing that activity since baseline.

7.1.10 Qualitative Interview

Effective with the implementation of Protocol Version 8.0 (Substantial Amendment 7), qualitative interviews will no longer be conducted. Participants will complete qualitative audio interviews remotely to collect direct feedback about their experience in the study, particularly with respect to treatment and changes in disease burden.

Trained interviewers will conduct the interviews using a semi-structured interview guide in a secure telemedicine platform.

7.2 Safety Assessments

Study procedures and their timing are summarized in the schedule of assessments [Table 1]. Protocol waivers or exemptions are not allowed. Procedures conducted as part of a participant's routine clinical management (i.e., standard of care) obtained before signing the ICF may be utilized for screening or baseline purposes, provided the procedures met the protocol-specified criteria and were performed within the timeframe, as defined in the schedule of assessments [Table 1].

7.2.1 Laboratory Assessments

- See [Section 10.6, Appendix 6: Clinical Laboratory Assessments] for the list of clinical laboratory tests to be performed and refer to schedule of assessments [Table 1] for timing and frequency.
- At follow-up phone call visits, a blood sample for abbreviated biochemistry will be collected at the participant's home by a qualified healthcare provider from the home healthcare vendor. In addition, at week 2, a blood sample for abbreviated biochemistry and hematology will be collected. These samples should be collected at the participant's home. In case the home healthcare visit is not feasible, the visit can be conducted at the study site. The detailed procedures will be described in the lab manual.
- The investigator or subinvestigator must review the laboratory report, document this review and record any clinically significant changes occurring during the study as an AE. The laboratory reports must be filed with the source documents.
- Clinical significance of out-of-range laboratory findings is to be determined and documented by the investigator or subinvestigator who is a qualified physician. Abnormal laboratory findings associated with the underlying disease are not considered clinically significant unless judged by the investigator to be more severe than expected for the participant's condition.

7.2.2 Vital Signs

- Body temperature, pulse and blood pressure will be assessed as outlined in the schedule of assessments [Table 1].
- Blood pressure (systolic blood pressure and diastolic blood pressure) and pulse measurements will be measured using a semiautomatic blood pressure recording device with an appropriate cuff size (same cuff size and same arm will be used for each time point).
- When vital signs are scheduled for the same time as a blood sample, the vital signs will be taken before the blood sample.
- Blood pressure and pulse will be measured in the sitting or supine position after the participant has rested for at least 5 minutes.

7.2.3 Physical Examination

- Physical examinations will be conducted at study site visits as outlined in the schedule of assessments [Table 1]. Body systems to be evaluated include general appearance, skin, lymphatic, head and neck, ears, nose and throat, chest and lungs, cardio-vascular, abdomen, extremities, musculoskeletal and neuromuscular. Any clinically relevant abnormality at screening, including baseline symptoms for mitochondrial myopathy should be recorded as medical history.
- Any clinically relevant change from baseline to the end of study will be recorded as an AE in the CRF.

7.2.4 Electrocardiogram

- A standard 12-lead ECG will be conducted as outlined in the schedule of assessments [Table 1] using both a central ECG reading laboratory and local ECG reading. ECGs at weeks 2 and 8 will be performed at the participant's home by a qualified healthcare provider from the home healthcare vendor. In case the home healthcare visit is not feasible, the visit can be conducted at the study site.
- ECGs will be recorded in triplicate (3 separate ECGs, 5 minutes resting prior to first ECG and at least 1 minute apart per time point), prior to blood draw and transmitted electronically for central reading. The mean of the triplicate ECG from central and local read should be used for treatment decisions and AE reporting.
- If the mean triplicate QTcF is > 500 msec at any time point, one follow-up triplicate ECG may be performed on the same day. If the follow-up mean QTcF is \leq 500 msec, the participant may proceed with IP. If the follow-up mean QTcF > 500 msec is confirmed, then the participant must discontinue IP.
- An ECG will also be performed within 24 hours of any of these events: an elevation of cTnI above the ULN (see Appendix 10.9 for reference range), or when there is an elevation of cTnT above the ULN (see Appendix 10.9 for reference range) or above the participant's baseline value if it was elevated, or when a participant has any signs or symptoms reflecting cardiac involvement, inclusive of new onset shortness of breath. If the ECG is within normal limits, a repeat of the abnormal troponin value (cTnI or cTnT) should be obtained. For any of the situations above, it may be required to interrupt or discontinue further administration of IP as described in [Section 8.1 Discontinuation of Individual Participant(s) from Study Treatment]. Participants with persistent cTnI or

cTnT elevations, abnormal ECG or abnormal echocardiogram should undergo cardiology follow up.

7.2.5 Echocardiogram

A local echocardiogram is to be performed within 24 hours of any of these events: an elevation of cTnI above the ULN (see Appendix 10.9 for reference range), or when there is an elevation of cTnT above the ULN (see Appendix 10.9 for reference range) or above the participant's baseline value if it was elevated, or when a participant has any signs or symptoms reflecting cardiac involvement, inclusive of new onset shortness of breath. If the echocardiogram is within normal limits, a repeat of the abnormal troponin value (cTnI or cTnT) should be obtained. For any of the situations above, it may be required to interrupt or discontinue further administration of IP as described in [Section 8.1 Discontinuation of Individual Participant(s) from Study Treatment]. Participants with persistent cTnI or cTnT elevations, abnormal ECG or abnormal echocardiogram should undergo cardiology follow up.

7.2.6 Body Weight

Body weight will be collected as outlined in the schedule of assessments [Table 1].

7.2.7 Columbia-Suicide Severity Rating Scale

- The C-SSRS was developed as a screening tool to identify suicide risk. The interviewer asks participants detailed questions regarding suicidal ideation, behaviors, intensity of ideation and attempts. Response options and recall periods vary in accordance with the nature of the question.
- The C-SSRS will be performed by trained site staff via interview as outlined in the schedule of assessments [Table 1]. At screening, the "Screening" version is to be used to determine eligibility. During all subsequent visits, the "Since Last Visit" version is used to monitor on study suicidal ideation and behavior after the initial assessment. If possible, continuity of raters should be maintained across visits for each participant.
- Participant who has a history of suicide attempt, suicidal behavior or has any suicidal ideation within 1 year prior to screening that meets criteria at a level of 4 or 5 by using the C-SSRS or who is at significant risk to commit suicide, as assessed by the investigator at screening will be excluded.

7.2.8 Order of Assessments

It is recommended that the participants follow the following order of assessments within each of the given visits [Table 6] to fulfill the requirements in the protocol.

Sponsor: API

- CONFIDENTIAL -

	(1	/
Week 0	Week 4	Week 12	Week 24
 Vital signs 	 Vital signs 	 Vital signs 	 Body Weight
 3 separate 12-lead ECG 	 3 separate 12-lead ECG 	 3 separate 12-lead ECG 	 Vital signs
-		-	• 3 separate 12-lead ECG
 Hematology, biochemistry, urinalysis 	 Hematology, biochemistry, urinalysis 	 Hematology, biochemistry, urinalysis 	 Hematology, biochemistry, urinalysis
 Serum and urinary biomarkers 	 Pregnancy test 	 Serum and urinary biomarkers 	 Serum and urinary biomarkers
 Pregnancy test 		 Pregnancy test 	 Pregnancy test
 Blood sample collection predose for genotyping 		 Blood for plasma pharmacokinetics at predose (-90 min to 0 min)* 	 Blood for plasma pharmacokinetics at predose
 Blood sample collection predose for PGx (banking) 		 Blood for pharmacodynamics (PPARδ target gene expression) at predose (-90 min to 	 Blood for pharmacodynamics (PPARδ target gene expression) at predose
 Blood sample collection predose for pharmacodynamics (PPARδ target gene expression) 		0 min)*	
• 6MWT	• 6MWT	• 6MWT	• 6MWT
 Patient reported outcomes 	 Patient reported outcomes 	 Patient reported outcomes 	 Patient reported outcomes
 C-SSRS 	 C-SSRS 	 C-SSRS 	 C-SSRS
 5XSTS 	• 5XSTS	• 5XSTS	 5XSTS
 Physical examination 	 Physical examination 	 Physical examination 	 Physical examination
 Verify inclusion/ exclusion criteria 	 Dispense IP 	Dispense IP	
 Randomization 	IP dosing	IP dosing	
Dispense IP		 Blood for plasma pharmacokinetics at postdose (0.5-4 h) 	
IP dosing			
 Blood for plasma pharmacokinetics at postdose (0.5-4 h) 			

Table 6Order of Assessments under Protocol Version 9.0 (Substantial Amendment 8 and Subsequent Versions)

5XSTS: 5 Times Sit to Stand; 6MWT: 6-minute walk test; C-SSRS: Columbia-Suicide Severity Rating Scale; ECG: electrocardiogram; IP: investigational product; PGx: pharmacogenomics; PPAR\delta: peroxisome proliferator-activated receptor delta

Note: Assessments in the same box may be performed in any order.

*Blood samples for pharmacokinetics and pharmacodynamics (PPAR δ target gene expression) at week 12 will be collected within 90 minutes prior to IP dosing. When it is not feasible to complete 6MWT, Patient reported outcomes, C-SSRS, 5XSTS and physical examination in 90 minutes, collect blood samples for pharmacokinetics and pharmacodynamics after the assessments to comply with the sample collection window.

7.3 Adverse Events and Other Safety Aspects

The definitions of an AE or SAE can be found in [Sections 10.3.1 and 10.3.2], respectively.

AEs will be reported by the participant (or, when appropriate, by a caregiver, surrogate or the participant's legally authorized representative).

The investigator and any qualified designees are responsible for detecting, documenting and recording events that meet the definition of an AE or SAE and remain responsible for following up AEs that are serious, considered related to the study IP or that caused the participant to discontinue the IP and/or study [see Section 10.3, Appendix 3: Adverse Events: Definitions and Procedures for Recording, Evaluating, Follow-up and Reporting].

The method of recording, evaluating and assessing causality of AE and SAE and the procedures for completing and transmitting SAE reports are provided in [Section 10.3 Appendix 3: Adverse Events: Definitions and Procedures for Recording, Evaluating, Follow-up and Reporting].

7.3.1 Time Period and Frequency for Collecting Adverse Event and Serious Adverse Event Information

All SAEs or AEs ([S]AEs) will be collected from the signing of the ICF until the follow-up visit or 28 days after the final IP administration, whichever is later, or when the participant is determined to be a screen failure, at the time points specified in the schedule of assessments [Table 1] and reported on the CRF.

If the severity of an (S)AE changes, the event should be relisted on the CRF with the new severity and new onset date.

If the severity decreases, the (S)AE should be relisted on the CRF with the new severity and new onset date. The exception is ongoing pre-dose events that continue post-dose and improve post-dose. Such events should not be re-listed.

If the severity of an SAE reduces, the details of the AE should be provided on the SAE worksheet for the medical assessor to be able to assess the course of the event.

All SAEs will be recorded and reported to the sponsor or designee immediately and under no circumstance should this exceed 24 hours, as indicated in [Section 10.3 Appendix 3: Adverse Events: Definitions and Procedures for Recording, Evaluating, Follow-up and Reporting]. The investigator will submit any updated SAE data to the sponsor within 24 hours of them being available.

Investigators are not obligated to actively seek AE or SAE after conclusion of the study participation. However, if the investigator learns of any SAE, including a death, at any time after a participant has been discharged from the study, and he/she considers the event to be reasonably related to the study IP or study participation, the investigator must promptly notify the sponsor.

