9.4.3.1 Adverse Events

AEs will be coded using MedDRA.

A TEAE is defined as below:

- For participants who consented for this study in Protocol Version 7.0 or former version and did not re-consent to Protocol Version 8.0 or later version by week 24: an AE observed after starting administration of the IP to 28 days after the last dose of IP for the double-blind treatment period of the study or moving to the OLE or day 182, whichever comes first.
- For participants who consented or re-consented to this study in Protocol Version 8.0 or later version by week 24: an AE observed after starting administration of the IP to 28 days after the last dose of IP for the double-blind treatment period of the study or moving to the OLE, whichever comes first.

The number and percentage of participants with TEAEs, SAEs, AEs leading to withdrawal of treatment and AEs related to IP will be summarized by SOC, PT and treatment group. The number and percentage of AEs by severity will also be summarized. The worst severity will be summarized if the same AE is recorded more than once for a participant.

An IP-related TEAE is defined as any TEAE with a causal relationship of "yes" by the investigator.

AE data will be listed.

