6.5.1 Adverse Events

AEs will be coded using the MedDRA.

An overview table will include the following:

- Number of TEAEs,
- Number and percentage of participants with TEAEs,
- Number of drug related TEAEs,
- Number and percentage of participants with drug related TEAEs,
- Number of serious TEAEs,
- Number and percentage of participants with serious TEAEs,
- Number of serious drug related TEAEs,
- Number and percentage of participants with serious drug related TEAEs,
- Number of TEAEs leading to death,
- Number and percentage of participants with TEAEs leading to death,
- Number of drug related TEAEs leading to death,
- Number and percentage of participants with drug related TEAEs leading to death,
- Number of TEAEs leading to withdrawal of study drug,
- Number and percentage of participants with TEAEs leading to withdrawal of study drug,
- Number of drug related TEAEs leading to withdrawal of study drug,
- Number and percentage of participants with drug related TEAEs leading to withdrawal of study drug, and
- Number of deaths.

Number of deaths is counted all reported deaths after starting administration of the IP. For participants who move to the OLE, all reported deaths after starting administration of the IP to moving to the OLE.

The number and percentage of participants with TEAEs, as classified by SOC, and PT will be summarized by analysis group. Summaries will be provided for the following:

- TEAEs,
- drug related TEAEs,
- serious TEAEs,
- drug related serious TEAEs,
- TEAEs leading to withdrawal of study drug,
- drug related TEAEs leading to withdrawal of study drug,
- TEAEs excluding Serious AEs that equal to or exceed a threshold of 5.0% in any analysis group.

The number of TEAEs and the number and percentage of participants with TEAEs, as classified by SOC and PT will be summarized by severity and by relationship to study drug. In the participant count, if a participant has multiple TEAEs with the same SOC or PT, but with differing severity or relationship, then the participant will be counted once with the worst severity and highest degree of relationship. If severity or relationship is missing for all episodes of the event, the participant will be counted under missing severity or relationship.

The following AESIs are defined:

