5.2 Safety Endpoints

5.2.1 Treatment Emergent Adverse Events (TEAEs)

AE collection begins after the ICF has been signed and continues until the follow up visit or 28 days after the final IP administration or when the participant is determined to be a screen failure. A TEAE is defined as an AE observed after starting administration of the ASP0367 to 28 days after the last dose of ASP0367.

An IP-related TEAE is defined as any TEAE with a causal relationship of "yes" by the investigator.

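### Relisting an AE when its severity falls can make an improving placebo-period event an ASP0367 TEAE in the 76-week SAP, and neither SAP says how relisted records enter event counts

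*Protocol*

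**What the plan says.** **Recording.** Protocol 7.3.1 gives a general rule for any change in severity: "the event should be relisted on the CRF with the new severity and new onset date". A further sentence applies the same to decreases. One carve-out follows: "The exception is ongoing pre-dose events that continue post-dose and improve post-dose"; these are not relisted. The section does not say which dose *pre-dose* refers to.

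**Treatment emergence.** In the 76-week SAP, 5.2.1: "A TEAE is defined as an AE observed after starting administration of the ASP0367", with the window closing 28 days after the last ASP0367 dose. It does not require the event to be new or to have worsened. In the 52-week SAP, 5.4.1, the window opens at first investigational product and closes 28 days after the last double-blind dose or at the move to the OLE, whichever is earlier.

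**Counting.** In both SAPs, 6.5.1, the overview table starts with "Number of TEAEs" and gives event counts for the related, serious, fatal and withdrawal subsets. Both also state: "The number of TEAEs and the number and percentage of participants with TEAEs, as classified by SOC and PT will be summarized by severity". The same breakdown is made for relationship. The rule for repeats is written for the participant count: when a participant has several TEAEs under one SOC or PT, "then the participant will be counted once with the worst severity and highest degree of relationship". Protocol 9.4.3.1 adds, for the severity summary: "The worst severity will be summarized if the same AE is recorded more than once for a participant".

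**Groups.** The 76-week SAP (4.1 and 6.1) keeps placebo participants who entered the OLE as their own group, Placebo to ASP0367.

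**The concern.** A relisted record has a start date later than the event it belongs to. If treatment emergence is decided on that date, a falling grade looks like a new event. For a participant who switches from placebo, the false start can land after the first ASP0367 dose, so an event that began on placebo and was resolving is tabulated as emerging on the drug.

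The same records feed the event counts. With no rule for joining them, the reported number of TEAEs depends partly on how often grades move, not only on how many events occurred. The nature, frequency and severity of TEAEs form a primary safety endpoint, so the counting unit should be defined.

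**Working it through.** The documents give no AE count and no rate of grade change, so there is no stated figure to reproduce. The check is a trace through the TEAE windows, plus a formula with assumed inputs.

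**1. Is onset date what decides emergence?** The SAPs say *observed*, not *with onset*. But 6.8.2 of both SAPs imputes incomplete AE onset dates, and Protocol 9.5 says imputed dates settle whether an AE is treatment emergent. Onset date is therefore the likely operating key. This is an inference, though a strong one.

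**2. Does the pre-dose exception apply to a switcher?** Protocol 6.1 and 6.3.1 make placebo part of the blinded investigational product. An event that starts on placebo is then already post-dose, and the exception does not reach it. If *pre-dose* instead meant before first ASP0367, the exception would apply. The first reading is the more natural one.

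**3. Trace of one placebo participant** (illustrative days; OLE starts on day 365, the scheduled week 52 day in SAP 6.8.1).

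| Course | 52-week SAP, placebo | 76-week SAP, Placebo to ASP0367 |
|---|---|---|
| Moderate on day 330, relisted as mild on day 380; pre-dose = before first product | 1 event | 1 event, 1 participant |
| Same course; pre-dose = before first ASP0367 | 1 event | 0 (not relisted) |
| Same course, with a new-or-worse rule | 1 event | 0 |
| Mild on day 330, moderate on day 380 | 1 event | 1 event, 1 participant, correctly |

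The once-per-SOC/PT rule gives no protection in the first row when the relisted record is that participant's only one in the window.

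**4. What one participant can do.** The 76-week SAP (6.5.1) has a table of non-serious TEAEs reaching 5.0% in any group. The size of the switcher group is not stated. Assume 11 (one third of the 33 interim participants, 33/3) to 22 (the planned arm): one participant is 1/11 = 9.1% to 1/22 = 4.5%. Since 1/20 = 5.0%, in any group of 20 or fewer a single misclassified participant puts a term in that table.

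**5. Event counts if each record is counted.** With *f* the share of events that change grade and *m* the changes in each such event, both assumed:

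records per 100 events = 100 × (1 + *f* × *m*)

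| *f* | *m* = 1 | *m* = 2 |
|---|---|---|
| 10% | 110 | 120 |
| 20% | 120 | 140 |
| 30% | 130 | 160 |
| 50% | 150 | 200 |

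A single event going mild, moderate, mild gives 3 records. Within one period, the number of participants with that PT stays at 1.

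**The case against.** Four points on the other side carry weight.

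- **Silence is not a counting rule.** A reader might infer that the SAPs count every record. Neither says so; they leave the unit for event counts undefined. This stands. It is also true that a collapsing rule written only for participants points towards uncollapsed event counts.
- **Existing safeguards.** A reader might infer that TEAE results are inflated throughout. They are not. Within a period, participant numbers and percentages are protected by the once-per-SOC/PT rule, and the protocol's worst-severity sentence limits the severity summary. Relisting applies to every arm, so no direction of between-arm bias can be claimed. The OLE route cannot touch the placebo-controlled comparison, because the 52-week window closes at the move to the OLE.
- **Temporal, not causal.** A reader might take the misclassified events as judged to be caused by ASP0367. TEAE status is about timing; causality is a separate investigator judgement with its own tables. The 76-week analysis is descriptive, and the affected group has its own labelled column.
- **Governing text.** Section 5.2.3 of the 76-week SAP says all participants were under protocol version 7.0 or earlier. The relisting wording here is from version 9.0, which has no OLE. The version 9.0 change log does not list Section 7.3.1, but what version 7.0 said cannot be confirmed.

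These points narrow the finding. They do not remove the missing new-or-worse test in the 76-week definition, nor the undefined meaning of *pre-dose* for a switcher.

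**Conclusion.** The point holds in a limited form and should be corrected.

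For switchers, the relisting rule and the 76-week TEAE definition together give a wrong result: an event that only improves after the switch counts as 1 ASP0367 TEAE and can add 1 participant, where it should count as 0. That also defeats the evident purpose of the pre-dose exception. The conclusion assumes that *pre-dose* means before first investigational product, that emergence is decided on onset date, and that the relisting rule applied to these participants. Events that worsen after the first ASP0367 dose are rightly treatment emergent and are not part of the problem.

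For event counts, both SAPs allow one event to be counted more than once. The size depends on a rate of grade change that the documents do not give; the table above shows a range, not an estimate.

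**What to change.** The order of the two steps matters.

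1. **Treatment emergence first, record by record.** In the 76-week SAP, count a switcher's continuing event as an ASP0367 TEAE only if it is new or its severity increased after the first ASP0367 dose, and define *pre-dose* for switchers as before first ASP0367. In the 52-week SAP, apply the same new-or-worsened test relative to first investigational product, in all arms alike.
2. **Linking second, for event counts only.** Join contiguous treatment-emergent records of the same event within a treatment period into one episode at its worst severity. Keep the date of on-treatment worsening as its treatment-emergent onset.

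Merging records to the earliest onset and worst severity before step 1 should be avoided: an event that began on placebo and worsened on ASP0367 would then carry a placebo-period date and could drop out of the ASP0367 tables.

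The cost is a modest amount of extra derivation in the AE dataset and slightly lower event counts, with no new data. Both SAPs (Section 1) provide for changes to the final planned analyses to be documented in the CSR, so the rule can be recorded there if the SAPs are not reissued.
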